2.2. Therapeutic Rationale

Since acromegaly is due to excessive GH and IGF-1 action, the goal is to suppress this pathway. As a matter of fact, normalization of circulating IGF-1 is a surrogate endpoint for the treatment of acromegaly. Inhibition of GH signaling results in suppression of IGF-1 secretion (Rowland et al. 2005). This can be achieved by suppressing the action of GHR. Clinical evidence that this mechanism lowers IGF-1 levels comes from studies conducted with Somavert (pegvisomant) and

[figure not shown]
ATL1103. Somavert is a human GHR antagonist that competes with endogenous GH for binding to its receptor and blocks production of IGF-1, and can normalize IGF-1 in ~63% of patients. However, Somavert dosing regimen is inconvenient for patients as it requires daily administration by SC injection and it may also cause elevations in circulating GH levels and in liver transaminases ([Melmed 2006](#)). Additionally, clinical evidence of a reduction in IGF-1 levels by GH inhibition is supported by studies conducted with the antisense drug ATL1103 (an antisense inhibitor of GHR) in which ATL1103, by reducing GHR, reduced serum IGF-1 levels by 26% after 13 weeks of dosing ([Trainer et al. 2018](#)).

[figure not shown]

[figure not shown]
[figure not shown]
In addition, since mature GHR is cleaved to produce the circulating GHBP which binds to circulating GH and prolongs its half-life ([Fisker 2006](#)),

2.3. ISIS 766720

[figure not shown]

[figure not shown]

2.3.4. Clinical Experience

Detailed information concerning the clinical studies conducted with ISIS 766720 can be found in the Investigator's Brochure. A summary is included below.

[figure not shown]

2.5. Benefit-Risk Assessment

Detailed information concerning the benefit-risk assessment of ISIS 766720 can be found in the Investigator's Brochure.

2.5.1. Benefit Assessment

The benefits of ISIS 766720 are unknown at this time.

3. EXPERIMENTAL PLAN

3.1. Study Design

This will be a Phase 2, randomized, open label multi-center study.

3.2. Number of Study Centers

This study will be conducted at multiple centers worldwide.

3.3. Number of Patients

Approximately 40 patients are planned to be randomized in the study. Thirty-six (36) patients (12 in each treatment group) in the per protocol set (PPS) are needed to complete the Treatment Period and the primary efficacy endpoint. [REDACTED]

[REDACTED]

3.4. Overall Study Duration and Follow-up

The study for an individual patient will generally consist of the following periods:

- A ≤ 6-week Screening Assessment Period
- A 73-week Treatment Period: ISIS 766720 will be administered as a once-monthly SC injection (except during Month 1 where a booster dose is administered on Day 15). The primary endpoint will be evaluated at 6 months (Week 27)
- A 14-week Post-Treatment Evaluation Period

Patients may be required to attend additional visits for monitoring of AEs or abnormal investigation results. The frequency of additional monitoring will be determined by the Sponsor Medical Monitor or Designee in consultation with the Investigator.

3.4.1. Screening

Patient eligibility for the study will be determined within 42 days prior to study entry. Sponsor Medical Monitor or Designee review is required for patients to enter the Treatment Period.

3.4.2. Treatment

Eligible patients will report to the Study Center for ISIS 766720 administration per Schedule of Procedures in [Appendix A](#). ISIS 766720 will be dosed monthly (in addition, a booster dose of ISIS 766720 is administered on Day 15). Please refer to Section [6.1.2](#) and [Appendix A](#) for detailed instructions regarding treatment requirements.

3.4.3. Post-Treatment

Patients are to return to the Study Center for follow-up visits for 14 weeks after last injection of ISIS 766720 per Schedule of Procedures in [Appendix A](#). Any patient who receives at least 1 dose of ISIS 766720 will be required to complete the Post-Treatment Period. The final study visit will be 14 weeks after the last injection (PTWk15).

4. PATIENT ENROLLMENT

4.1. Screening

[figure not shown]
Before patients may be enrolled into the study, the Sponsor or Designee requires a copy of the Study Center's written independent ethics committee/institutional review board (IEC/IRB) approval of the protocol, informed consent form (ICF), and all other patient information and/or recruitment material.

Patients or their legally acceptable representatives must sign the consent form before any screening tests or assessments are performed. At the time of consent, the patient will be considered enrolled into the study and will be assigned a unique screening number before any study procedures, including Screening procedures, are performed. At the time of randomization, patients will be assigned a unique patient identification number. This number will be used to identify the patient throughout the trial and must be used on all study documentation related to that patient. The screening number and patient identification number must remain constant

throughout the entire trial. In the event the patient is re-consented and re-screened the patient must be given a new screening number. Screening numbers and patient identification numbers, once assigned, will not be re-used.

4.2. Randomization

Patients will be randomized after all Screening assessments have been completed, after the Investigator has verified that they are eligible per criteria in Sections [5.1](#) and [5.2](#), and after review by the Sponsor Medical Monitor or Designee. No patient may begin treatment prior to randomization and assignment of a unique patient identification number.

4.3. Replacement of Patients

Patients who withdraw from the study will not be replaced.

5. PATIENT ELIGIBILITY

To be eligible to participate in this study candidates must meet the following eligibility criteria at the time point specified in the individual eligibility criterion listed.

5.1. Inclusion Criteria

1. Must have given written informed consent (signed and dated) and any authorizations required by local law and be able to comply with all study requirements
2. Males or females with a documented diagnosis of Acromegaly* who are 18 to 75 years old (inclusive) at the time of informed consent

* Defined as a previous diagnosis of GH-secreting adenoma by surgical pathology; or the presence of a pituitary adenoma identified on magnetic resonance imaging (MRI) or computed tomography (CT) Scan (if MRI is contraindicated) and serum IGF-1 levels above the upper limit of normal (ULN) for age and sex at time of diagnosis (serum IGF-1 level and imaging at diagnosis will be collected in the case report forms [CRF]).

3. Have had pituitary surgery (e.g. transsphenoidal) unless there was a contraindication to surgery **and** are either acromegaly medical treatment naïve, or who had not taken any other acromegaly medications prior to the screening visit as outlined below:

bromocriptine: 2 weeks

cabergoline: 4 weeks

quinagolide: 4 weeks

octreotide daily injection (SC) or oral formulation: 4 weeks

pegvisomant: 4 weeks

octreotide LAR: 3 months
pasireotide LAR: 4 months
lanreotide (all formulations): 3 months

4. At Screening, serum IGF-1 (performed at central lab) between 1.3 to $5 \times$ ULN, inclusive, adjusted for age and sex. IGF-1 can be repeated once and averaged to determine eligibility if the initial result is between 1.1–1.3 \times ULN, or between 5–5.3 \times ULN
5. Females must be non-pregnant and non-lactating, and either:
 - a. surgically sterile (e.g., tubal occlusion, hysterectomy, bilateral salpingectomy, bilateral oophorectomy)
 - b. post-menopausal (defined as 12 months of spontaneous amenorrhea in females > 55 years of age or, in females ≤ 55 years, 12 months of spontaneous amenorrhea without an alternative medical cause and follicle-stimulating hormone (FSH) levels in the postmenopausal range for the laboratory involved)
 - c. abstinent (defined in Section 6.3.1) or
 - d. Women of childbearing potential (WOCBP) should agree to taking all precaution to avoid pregnancy during the Trial Period (including Post-Treatment), including agreeing to receive pregnancy testing before each monthly dose, using 1 highly effective method of birth control (Section 6.3.1) from the time of signing the (ICF) until 14 weeks after the last dose of ISIS 766720 administration

Males must be either:

- e. surgically sterile
- f. abstinent (defined in Section 6.3.1) or
- g. if engaged in sexual relations with a female of child-bearing potential, the patient must be using a highly effective contraceptive method (refer to Section 6.3.1) from the time of signing the ICF until 14 weeks after the last dose of ISIS 766720

6. Willing to refrain from strenuous exercise/activity (for example heavy lifting, weight training, intense aerobics classes etc.) for at least 24 hours prior to study visits
7. Willing to refrain from alcohol or tobacco use for 8 hours prior to study visits

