6.3. Restriction on the Lifestyle of Patients

6.3.1. Contraception Requirements

All male patients and WOCBP must refrain from sperm/egg donation and practice highly effective contraception from the time of signing the ICF until 14 weeks after their last dose of study treatment.

Male patients engaged in sexual relations with a female of child-bearing potential must use highly effective contraception from the time of signing the informed consent until 14 weeks after the patient's last dose of study treatment. If the patient's non-pregnant female partner is using a highly effective contraception method throughout the duration of the study, the requirement for contraception for the male patient is considered fulfilled.

For the purposes of this study, WOCBP are defined as any female who has experienced menarche, and who does not meet 1 of the following conditions:

- Postmenopausal: 12 months of spontaneous amenorrhea in females > 55 years of age or, in females ≤ 55 years, 12 months of spontaneous amenorrhea without an alternative medical cause and FSH levels in the postmenopausal range for the laboratory involved
- 6 weeks after surgical bilateral oophorectomy with or without hysterectomy
- Post hysterectomy

For the purposes of the study, highly effective contraception is defined as follows:

For male patients:

- a vasectomy with negative semen analysis at Follow-up
- sexual abstinence[†]
- Male patients with partners that are pregnant must use condoms to ensure that the fetus is not exposed to the ISIS 766720

For female patients of childbearing potential:

- surgical sterilization (e.g., bilateral tubal occlusion), hormonal contraception associated with inhibition of ovulation (combined [estrogen and progestogen containing] or progestogen-only), intrauterine device (IUD), intrauterine hormone-release system (IUS), a vasectomized partner or sexual abstinence[†]

[†] **Note:** Abstinence is only acceptable as true abstinence, refraining from heterosexual intercourse throughout the duration of study participation. Periodic abstinence (e.g., calendar, ovulation, symptothermal, post-ovulation methods), declaration of abstinence for the duration of a trial and withdrawal are not acceptable methods of contraception.

Note: A female condom and a male condom should not be used together as friction between the 2 can result in either or both products failing.

[figure not shown]

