- ⁷ A pregnancy test is required at Screening for all female patients who are of childbearing potential regardless of age. Serum at Screening, and dipstick is acceptable after Screening. FSH is required to confirm menopause for women ≤ 55 years who have 12 months of spontaneous amenorrhea with no alternative medical cause, and who are not surgically sterile. For patients requiring confirmation of menopause at Screening per protocol, a pregnancy test and FSH are required at Screening, however, once menopause status is confirmed, a pregnancy test is not required in subsequent visits. If patient is surgically sterile, no pregnancy test or FSH is required
- ⁸ Fasting is not required at Screening Visit. For all other visits, fasted samples should be taken after fasting for 8 hours. During this time the patient can drink water and they should ensure that they consume enough water to not become dehydrated
- ⁹ If the platelet value, serum creatinine or liver enzyme tests are uninterpretable (e.g., due to clumping, hemolysis or quantity not sufficient) or missing, the test must be repeated and a result not meeting stopping rule must be obtained prior to next dose. Platelets require a valid result from the prior platelet test within 21 days up to week 17 and within 35 days after week 17 (per Section 8.5.2). In consultation with the medical monitor or designee, a local lab and central lab should be drawn and evaluated prior to dosing (per Section 6.2.1)
- ¹⁰ A morning cortisol sample is required, and the sample should be drawn prior to 9:00 AM. For patients on stable glucocorticoid therapy, the cortisol sample may be taken at any time
- ¹¹ Patient should fast for 10 hours prior to OGTT. OGTT Sample Time Schedule: 0, 30, 60, 90, 120 mins. After the 120-min blood draw, the fasting period is completed. See Section 6.2.2 procedure details

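### Non-postmenopausal women with tubal occlusion or bilateral salpingectomy are of childbearing potential under protocol Section 6.3.1, yet the Appendix A footnotes waive their pregnancy tests

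*Combined protocol and SAP*

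**What the plan says.** Four places in the protocol bear on this.

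- **Section 5.1, criterion 5a (repeated in the synopsis).** One route to eligibility for a woman is to be "surgically sterile (e.g., tubal occlusion, hysterectomy, bilateral salpingectomy, bilateral oophorectomy"). Criterion 5d is a separate route for women of childbearing potential (WOCBP), who agree to a pregnancy test before each monthly dose.
- **Section 6.3.1.** "For the purposes of this study, WOCBP are defined as any female who has experienced menarche" and who meets none of three conditions. One is postmenopausal status. The two surgical conditions are "6 weeks after surgical bilateral oophorectomy with or without hysterectomy" and "Post hysterectomy". The same section's list of highly effective methods for women of childbearing potential begins with "surgical sterilization (e.g., bilateral tubal occlusion), hormonal contraception associated with inhibition of ovulation".
- **Appendix A, treatment-period footnote 7.** It opens "A pregnancy test is required at Screening for all female patients who are of childbearing potential regardless of age". It then asks for FSH to confirm menopause in women aged 55 or under who have "12 months of spontaneous amenorrhea with no alternative medical cause, and who are not surgically sterile". It closes "If patient is surgically sterile, no pregnancy test or FSH is required".
- **Appendix A, post-treatment footnote 6.** It waives later pregnancy tests for a patient who is surgically sterile or whose menopause was confirmed at Screening.

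**The concern.** Testing is switched on by one term (WOCBP) and off by another (surgically sterile), and the two overlap. Section 6.3.1 defines the first. The footnotes do not define the second, and the only list of female procedures under that name is in criterion 5a, where a site would naturally look.

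At stake is whether a woman who is WOCBP by the study's definition is routinely tested before she receives an investigational antisense drug. The protocol takes pregnancy seriously elsewhere: Section 8.8 makes it a reason for permanent discontinuation, and Section 9.5.4 sets a 24-hour limit for submitting the pregnancy form. Sites that read the footnote differently would also handle the same patient differently.

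**Working it through.** No figure in the plan has to be reproduced. The check applies each text in turn to a post-menarche, non-postmenopausal woman whose only relevant surgery is the one named.

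| Surgery | Surgically sterile (5a)? | WOCBP (6.3.1)? | Footnote 7, opening | Footnote 7, close |
|---|---|---|---|---|
| Tubal occlusion | Yes, named | Yes: not an exception, and named as a method for WOCBP | Test required | Test waived |
| Bilateral salpingectomy | Yes, named | Yes: not an exception, and fits the open-ended surgical sterilization entry | Test required | Test waived |
| Bilateral oophorectomy, 6 weeks or more ago | Yes, named | No | Not triggered | Test waived |
| Hysterectomy | Yes, named | No | Not triggered | Test waived |

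The first two rows are the problem, and the last two are consistent. Salpingectomy has the same status as tubal occlusion, because the method entry in Section 6.3.1 gives tubal occlusion only as an example.

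Footnote 7 can be read in two ways for the first two rows.

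1. *Two rules of equal standing.* The opening requires the Screening test and the close waives it.
2. *General rule, then exception.* The close prevails and no test is required. The footnote is then coherent, but it exempts a woman whom Section 6.3.1 defines as WOCBP.

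On the second reading, and on the first if a site follows the closing sentence, she can reach Day 1 without a routine test.

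The other safeguards do not fill the gap. The stem of criterion 5 requires every female to be non-pregnant but names no test. Section 6.1.1 has the Medical Monitor or Designee review eligibility, without saying what evidence is needed here. Section 9.5.4 requires a test once pregnancy is suspected, which does not find an unsuspected one.

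**Size.** The documents do not say how many such women will enrol. I assume 0 to 3 among about 40 patients.

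- Test both required and waived within footnote 7: 1 (Screening) per woman, so 0 × 1 = 0 to 3 × 1 = 3 in the trial.
- Tests that the fix would add, counting Screening, dosing days and post-treatment visits:
  - Monthly doses run from Day 1 to Day 505 every 28 days: 504/28 + 1 = 19, or 20 with the Day 15 booster.
  - There are 3 post-treatment visits (PTWk5, PTWk9, PTWk15).
  - Per woman completing treatment and follow-up: 1 + 19 + 3 = 23, or 1 + 20 + 3 = 24 with the booster. Over 0 to 3 women this is 0 to 3 × 24 = 72.

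The second count is a floor. The pregnancy-test row in Appendix A also marks some non-dosing visits, such as Weeks 7, 11 and 15.

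**The case against.** The strongest defence is that footnote 7 is a rule followed by its exception, that footnote 6 makes a similar exception, and that a site therefore has one workable answer: no test is required. This largely stands against the stronger claim a reader might make, that the footnote is a flat contradiction which cannot be followed. It does not explain why women whom Section 6.3.1 keeps inside the WOCBP definition should be exempt, and the opening sentence speaks of all patients of childbearing potential.

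Meeting criterion 5a while being WOCBP is also not an error in itself. The routes in criterion 5 overlap: an abstinent premenopausal woman entering under 5c is WOCBP too. The agreement to monthly testing is written only into 5d, so it does not bind a woman who enters under 5a. For that reason the later tests should not be described as required and waived in the way the Screening test is. Footnote 6 holds only a waiver.

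Section 6.3.1 could instead be changed to exempt tubal occlusion and salpingectomy. That would also make the text consistent, and the choice is partly judgement. I prefer to keep Section 6.3.1, because it is the stated study definition and deliberately lists tubal sterilization among methods for women who remain of childbearing potential.

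Finally, these women have a method that the protocol accepts as highly effective, and a test that is not required is not forbidden. Both points are true, and they are why the matter is minor.

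**Conclusion.** The point holds as a minor inconsistency with a small safety consequence. A non-postmenopausal woman with tubal occlusion or bilateral salpingectomy is WOCBP under Section 6.3.1, and the footnote waivers allow her to be dosed without a routine pregnancy test. This rests on taking surgically sterile in the footnotes to mean what criterion 5a says it means. If the sponsor intended a narrower meaning, the text should say so.

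The number of women affected is unknown and may be zero; 0 to 3 is my assumption. A reader might infer that such women are ineligible, inadequately protected by contraception, or a threat to the results. The documents support none of these. The women qualify under 5d, their procedure meets the contraception requirement, and no endpoint or analysis depends on the test. On FSH, the panel for the pituitary axis in Appendix B includes it for females anyway, so only the wording needs aligning.

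**What to change.** Let Section 6.3.1 govern.

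1. In criterion 5a and the synopsis, replace the open example list by *surgically sterile by hysterectomy or bilateral oophorectomy, per Section 6.3.1*. State that non-postmenopausal women with tubal occlusion or bilateral salpingectomy enter under 5d, with that procedure as their highly effective method.
2. In footnote 7, make the closing waiver apply to a patient who is *not WOCBP per Section 6.3.1 because of hysterectomy or bilateral oophorectomy*. Align the FSH sentence by limiting it to women who are not already outside WOCBP for that reason.
3. In post-treatment footnote 6, replace surgically sterile with the same phrase as in item 2.
4. Keep the menopause-confirmation wording in both footnotes.

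The cost is wording in the synopsis, Section 5.1 and two footnotes. For each affected woman it adds one Screening serum test and dipsticks at visits already scheduled, on the count shown above. No visit is added and no patient loses eligibility.

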5.2. Exclusion Criteria

1. Clinically significant (CS) abnormalities in medical history according to Investigator judgement (e.g., previous acute coronary syndrome within 6 months of Screening, major non-pituitary surgery within 2 months of Screening) or from Screening physical examination (PE)
2. Patients who received surgery for pituitary adenoma within the last 3 months before the trial, and/or planning to receive surgery during the trial
3. Patients who received radiotherapy for pituitary adenoma within the last 2 years before the trial, and/or planning to receive radiotherapy during the trial
4. Patients with a pituitary tumor that, per Investigator judgment, is worsening (e.g., either growing, or at risk of compressing or abutting the optic chiasm or other vital structures) as assessed by pituitary/sellar MRI protocol at Screening or within 3 months of Screening. CT scan is allowed if MRI is contraindicated

5. Evidence of decompensated cardiac function per medical judgement and/or New York Heart Association (NYHA) Class 3 or 4
6. Clinical evidence of symptomatic hyperprolactinemia that would necessitate treatment
7. Symptomatic cholelithiasis, and/or choledocholithiasis
8. Intentionally left blank
9. Patients with history of hypoglycemia unawareness (who have had > 3 severe episodes in the past 6 months) or documented reactive hypoglycemia
10. Screening laboratory results as follows, or any other CS abnormalities in Screening laboratory values that would render a patient unsuitable for inclusion (abnormalities may be retested for eligibility purposes)
 - a. UPCR ≥ 500 mg/g. In the event of urine protein/creatinine ratio (UPCR) above this threshold eligibility may be confirmed by a quantitative total urine protein measurement of < 1000 mg/24 hr
 - b. Positive test (including trace) for blood on urinalysis. In the event of a positive test eligibility may be confirmed with urine microscopy showing ≤ 5 red blood cells per high power field
 - c. alanine aminotransferase (ALT) or aspartate aminotransferase (AST) $> 1.5 \times$ ULN; alkaline phosphatase (ALP) $> 3 \times$ ULN; Total bilirubin $\geq 1.5 \times$ ULN. Patients with Gilbert's syndrome may have total bilirubin $\geq 1.5 \times$ ULN if only the indirect bilirubin is elevated $>$ ULN and the ALT/AST is not greater than the ULN.
 - d. eGFR < 45 mL/min/1.73 m² as determined by the Chronic Kidney Disease-Epidemiological Collaboration (CKD-EPI) equation for creatinine clearance OR serum creatinine > 1.8 mg/dL in males and > 1.5 mg/dL in females
 - e. Platelet count $< 125,000$ mm³
 - f. Abnormal thyroid function tests must be discussed with the Sponsor Medical Monitor or Designee
 - g. HbA1c $> 10\%$
 - h. Abnormal morning cortisol test demonstrating symptomatic adrenal insufficiency based on Investigator judgement
11. Active infection requiring systemic antiviral or antimicrobial therapy that will not be completed prior to Study Day 1
12. Unwillingness to comply with study procedures, including follow-up, as specified by this protocol, or unwillingness to cooperate fully with the Investigator
13. Active infection with human immunodeficiency virus (HIV), hepatitis C (HCV) or hepatitis B (HBV) diagnosed by initial serology testing and confirmed with RNA testing, or prior treatment for HCV. Patients at Screening who test positive by serology, but negative by RNA may be allowed in consultation with the Sponsor Medical Monitor or Designee
14. Malignancy within 5 years, except for basal or squamous cell carcinoma of the skin, carcinoma *in situ* of the cervix, follicular Stage 1 or papillary thyroid cancer that has been successfully treated; patients that have been treated with curative intent and which have

no recurrence within 5 years may also be eligible if approved by the Sponsor Medical Monitor or Designee

15. Treatment with another investigational drug, biological agent, or device within 1 month of Screening, or 5 half-lives of investigational agent, whichever is longer
16. Treatment with any non-ION- or ISIS-oligonucleotide (including small interfering ribonucleic acid [siRNA]) at any time or prior treatment with an ION- or ISIS-oligonucleotide within 9 months of Screening. Patients that have previously received only a single-dose of an ION- or ISIS-oligonucleotide as part of a clinical study may be included as long as duration \geq 4 months has elapsed since dosing. This exclusion does not apply to vaccines (neither mRNA nor viral vector vaccines)
17. History of bleeding diathesis or coagulopathy
18. Recent history of, or current drug or alcohol abuse that could affect study compliance per Investigator judgment
19. Patients may not have chronic systemic use of weight loss medications (except GLP-1 agonist or SGLT2 inhibitors) or participate in weight loss programs within 2 months before Screening. Patients taking GLP-1 agonist or SGLT2 inhibitors indicated for weight loss may be allowed with prior consultation with the Sponsor Medical Monitor or Designee
20. Patients on anti-diabetes medications must be on a stable dose and regimen for \geq 3 months prior to Screening. Patients taking insulin can be allowed with prior consultation with the Sponsor Medical Monitor or Designee
21. Patients on estrogen containing medications must be on a stable dose and regimen for \geq 3 months prior to Screening
22. Patients on glucocorticoid replacement used for adrenal insufficiency must be on a stable dose and regimen (increases used to prevent adrenal crisis is permitted) for \geq 3 months prior to Screening
23. Use of oral anticoagulants, unless the dose has been stable for 4 weeks prior to the first dose of ISIS 766720 and regular clinical monitoring is performed during the trial
24. Blood donation of 50 to 499 mL within 30 days of Screening or of > 499 mL within 60 days of Screening and during the trial
25. Have any other conditions, which, in the opinion of the Investigator and Sponsor would make the patient unsuitable for inclusion, or could interfere with the patient participating in or completing the Study

